7.4. Planned Study Analyses

7.4.1. Statistical Summaries: Descriptive and Inferential

Safety and effectiveness endpoint results will be presented by treatment group (Deseyne [vifilcon C] and 1-Day Acuvue Moist [etafilcon A]).

All p-values will be rounded to and displayed in four decimals. If a p-value less than 0.0001 occurs, it will be shown in tables as <0.0001. The p-values for the analysis of effectiveness endpoints will be considered descriptive.

Descriptive summaries of variables will be provided where appropriate. For continuous variables, the number of non-missing values (n), mean, standard deviation, median, confidence intervals (CIs), minimum, and maximum will be tabulated by treatment group. Means, medians, and CIs will be presented with 1 more decimal place than the recorded raw data. Standard deviations will be presented with 2 more decimal places than the recorded raw data. Minima and maxima will be presented with the same number of decimal places as the recorded raw data. Values with magnitude <1 will be presented with a leading zero to the left of the decimal (e.g., 0.123).

Categorical data will be summarized using frequencies, percentages, and CIs. Percentages will be presented with 1 decimal place. Percentages may not be presented when the count is 0. Unless otherwise specified, the denominator for percentages will be the number of non-missing values within the group being presented.

All study-related data collected will be presented in listings. Study-related data not subject to analysis according to this plan will not appear in any tables or graphs but will be included in the data listings.

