Secondary effectiveness endpoints:	
Secondary effectiveness endpoints will include distance VA; symptoms/complaints and subjective assessments; lens wettability, centration, and movement; and lens deposits at each post-baseline visit and the satisfaction survey (modified Visual Functioning Questionnaire) at the Screening and Exit Visits.
			
Safety endpoints:	
The primary safety endpoint will be the proportion of eyes with any slit lamp findings (including corneal edema [epithelial, stromal], corneal infiltrates, corneal vascularization, corneal staining, palpebral conjunctival injection, and limbal injection) Grade >2 at any follow-up visit between the test and control lenses.
 
Secondary safety endpoints will include adverse reactions (serious and incidental), adverse device effects, pinhole VA (for eyes with a 2-line decrease in BCDVA or worse from baseline), conjunctival hyperemia as measured by the Cornea and Contact Lens Research Unit grading scale, keratometry, slit lamp biomicroscopy, spherocylindrical refraction, BCDVA, corneal fluorescein staining, lens discontinuation rates at any follow-up visit, and use of unpreserved lubricant eyedrops or artificial tears during the study.
			
Statistics:	
All analyses will be descriptive in nature. A full declaration of planned statistical analyses will be documented in a formal Statistical Analysis Plan.
			
Sample size:	
The sample size of approximately 80 subjects (160 eyes) is considered sufficient for evaluation of the clinical performance of the test and control lenses. The sample size was not based on statistical power considerations. A dropout rate of approximately 20% is expected;
			

	thus, approximately 60 subjects (120 eyes) are targeted to be described in this study.
--	--

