5.3. Randomization and Blinding

Subjects will be randomized to 1 of 2 treatment arms in a 2:1 ratio (test:control), wearing either test or control lenses in both eyes for the duration of the study. Randomization will be stratified by investigational site.

Subjects will be randomized after they are deemed eligible to participate, according to subject-specific randomization information provided by the randomization system.

This open-label study will not be masked.

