6. SAMPLE SIZE

The sample size of approximately 80 subjects (160 eyes) is considered sufficient for evaluation of the clinical performance of the test and control lenses. The sample size was not based on statistical power considerations. A dropout rate of approximately 20% is expected; thus, 60 subjects (120 eyes) are targeted to be described in this study.

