10. SAFETY ANALYSES

All safety analyses will be conducted using the SP. All safety analyses will be completed using the actual treatment a subject received. Observed case data will be used; no imputation will be performed for missing safety data except for the limited situations described in Section 7.3.2. Safety data will be tabulated and summarized descriptively by treatment group. Each eye will be treated independently for safety purposes.

All safety data will be presented in by-subject listings.

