10.3. Other Safety Variables

All safety variables are listed in Section 5.4.

Categorical safety variables will be summarized descriptively using counts and percentages for each treatment group at each visit.

For continuous safety variables, observed values and change from baseline will be summarized descriptively for each parameter (as appropriate) by treatment group at each visit.

For safety endpoints that assess each eye separately, each eye will be treated independently for summarizations.

Graded slit lamp findings will be assessed at each scheduled follow-up visit (1-Week, 1-Month, 2-Month, and 3-Month/Exit Visits) and, optionally, at unscheduled visits. The number and percentage of eyes with findings Grade >2 at any follow-up visit, including unscheduled visits, will be presented by treatment group. Corneal scar findings will not be tabulated but will be listed.

Pinhole VA results for eyes with a 2-line decrease in BCDVA or worse from baseline will be listed with the Distance logMAR VA data.

Lens discontinuation will be assessed at each scheduled follow-up visit (1-Week, 1-Month, 2-Month, and 3-Month/Exit Visits) and, optionally, at unscheduled visits. The time to discontinuation will be based on the study lens exposure weeks defined in Section 8.6. The lens discontinuation rate at each follow-up visit will be presented by treatment group.

The use of unpreserved lubricant eyedrops or artificial tears will be assessed for each follow-up visit by counting the number of drops recorded in the OTC Artificial Tears Log for the period between each visit.

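### A zero result on the primary safety endpoint could appear as a bare 0, or with an upper limit that treats paired eyes as independent and may be about half the subject-level limit

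*SAP*

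**What the plan says.** The Protocol synopsis defines the endpoint by eye: "The primary safety endpoint will be the proportion of eyes with any slit lamp findings" of Grade >2 at any follow-up visit. Five parts of the SAP bear on how it will be reported.

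- **Section 7.4.1, general rule:** "Categorical data will be summarized using frequencies, percentages, and CIs". No confidence level, sidedness or method is given here or elsewhere.
- **Section 7.4.1, same paragraph:** "Percentages may not be presented when the count is 0". This exception mentions percentages only.
- **Section 10.3, this endpoint:** "The number and percentage of eyes with findings Grade >2 at any follow-up visit, including unscheduled visits, will be presented by treatment group". The section's general rule is similar: "Categorical safety variables will be summarized descriptively using counts and percentages for each treatment group at each visit". Neither sentence mentions an interval.
- **Section 10:** "Each eye will be treated independently for safety purposes".
- **Section 5.3:** allocation is 2:1 test to control, and each subject wears the same lens type in both eyes.

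Section 5.2 gives about 53 test subjects (106 eyes) and 27 control subjects (54 eyes). Section 6 says "The sample size was not based on statistical power considerations". Section 9.1 reports the 5-letter endpoint as number and percentage by treatment group and eye, again without mentioning an interval.

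**The concern.** The trial is descriptive and was not sized for power. When few or no events are seen, the upper confidence limit is what tells the reader which event rates the data can exclude. The rules above leave two unsatisfactory outcomes open if an arm has no Grade >2 finding.

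1. **No limit at all.** If Section 10.3 is followed as the specific rule and the zero-count exception is used, the cell can contain a bare 0.
2. **A limit that is too low.** If the 7.4.1 interval is applied under the Section 10 independence rule, its denominator is eyes. The lens is assigned to the subject, and fellow eyes share the wearer, the lens type and the wearing habits, so their findings are likely to be correlated. Counting two eyes as two independent observations then overstates the information.

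Because of the 2:1 allocation, equal zeros do not mean equal evidence. The control arm can exclude only rates about twice as high as those the test arm can exclude. Two zero cells without limits would hide that.

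**Working it through.** **Inputs.** Total of 80 subjects allocated 2:1 (SAP 5.1, 5.3), and arm sizes from SAP 5.2. A two-sided 95% exact (Clopper-Pearson) interval is my assumption, since the SAP names no level or method.

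**Step 1: reproduce the arm sizes.** 80 × 2/3 = 53.3 and 80 × 1/3 = 26.7, which round to the SAP's 53 and 27. Two eyes each gives 106 and 54.

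**Step 2: upper limit for zero events.** For 0 of n the exact upper limit is 1 − 0.025^(1/n).

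| Unit | Control | Test |
|---|---|---|
| Eyes, treated as independent | 0/54: 6.6% | 0/106: 3.4% |
| Subjects, either eye affected | 0/27: 12.8% | 0/53: 6.7% |

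**Step 3: how the two rows relate.** If fellow eyes always agree, 54 eyes carry the information of 27 subjects and the limit is 12.8%. If they are independent, it is 6.6%. Partial correlation puts the control bound between 6.6% and 12.8%, and the test bound between 3.4% and 6.7%. The eye-level rate cannot exceed the proportion of subjects with either eye affected, so the subject-level limit is safe for both.

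**Step 4: sensitivity to the interval type.** For 0/27, Wilson gives 12.5%, the rule of three (3/n) gives 11.1%, and a one-sided 95% exact limit gives 10.5%. The choice among these matters less than the choice of unit. A normal-approximation interval is different in kind: its half-width is 1.96 × √(p(1−p)/n), which is 0 at p = 0 and at p = 1.

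**Step 5: how plausible is a zero?** The documents give no Grade >2 rate, so I take a range. P(0) = (1−p)^n.

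| Assumed rate | 27 subjects | 53 subjects | 54 independent eyes | 106 independent eyes |
|---|---|---|---|---|
| 1% | 76% | 59% | 58% | 34% |
| 2% | 58% | 34% | 34% | 12% |

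Zero is the single most likely count only if p < 1/(n+1). That threshold is 3.6% for 27 subjects, 1.9% for 53 subjects, 1.8% for 54 eyes and 0.9% for 106 eyes. Zero in both arms together has probability 0.99^80 = 45% at 1% per subject and 0.98^80 = 20% at 2%.

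**Step 6: the 5-letter endpoint.** It is reported separately for each eye, so the denominators are already about 27 and 53 and pairing is not an issue. If every eye succeeds, the exact lower limit is 0.025^(1/n): 87.2% for 27/27 and 93.3% for 53/53. A normal-approximation interval would read 100% to 100%.

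**The case against.** The strongest reply is that the zero-count sentence is a display convention. It covers the percentage only and sits in the same paragraph as the promise of intervals for categorical data. Section 10.3 does not repeat that promise, but does not withdraw it either. **This stands in part.** A reader might infer from the zero-count sentence that a zero result will carry no bound. The documents do not support that: a bare 0 is permitted, but so is a 0 with an interval.

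A reader might also take zero to be the likeliest result. The documents do not establish this. Excluding subjects with Grade 2 or higher at entry makes a low rate plausible, but no rate is stated. At an assumed 2% per subject, one event in the test arm (37%) is slightly more likely than none (34%).

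Third, the endpoint is defined by eye, so 12.8% and 6.7% are not on the plan's own unit. **This stands as a labelling point.** Both sets of limits belong side by side, and the eye-level count should stay. It does not rescue the independence rule, because lenses are assigned per subject.

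Fourth, a zero-width interval is hypothetical, since no method is named. **True.** An unnamed method alone would be only missing detail.

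Fifth, readers could calculate the bound themselves from the count and denominator. For a zero count they can, if the denominator is shown. For a non-zero count they cannot do so from the table: two affected eyes may be one subject or two.

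Finally, it may be tempting to quote limits on the 60 subjects targeted to remain. The endpoint counts any follow-up visit in the Safety Population, so subjects who leave after a follow-up examination still contribute. Completers are not its denominator.

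**Conclusion.** The point holds as a gap between Sections 7.4.1, 10 and 10.3. The stated rules allow the primary safety result, if zero, to appear without an interval, or with one based on eyes treated as independent. In the second case the upper limit can be about half the subject-level value: 6.6% against 12.8% in control, and 3.4% against 6.7% in test. The size of the understatement depends on the correlation between fellow eyes, which the documents do not give; it is nil if eyes are independent and largest if they always agree.

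The limits assume the planned arm sizes, follow-up data on every subject, and two-sided 95% exact intervals. The conclusion does not depend on zero being the expected result, because a plan should settle before the data are seen what it will show at zero.

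**What to change.** **SAP 10.3, Table 14.3.3.** Keep the eye-level count and percentage, so the protocol's endpoint is unchanged. State that n/N and the percentage are always shown, including at a zero count. Add the proportion of subjects with either eye affected, with an exact (Clopper-Pearson) two-sided 95% interval, also when the count is 0. Say that this interval is on subjects because both eyes wear the same lens, and that the Section 10 independence rule does not apply to it.

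**SAP 7.4.1 and 9.1, Table 14.2.2.x.** Name the same exact interval for the 5-letter endpoint, per eye as already planned, so that it remains valid at 100%.

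**Cost.** A few SAP sentences, one derived subject-level variable and an exact option in the table program. No new data or visits are needed. The drawback for the sponsor is that a zero-event result will look less favourable with its upper limit beside it.

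Intervals on every adverse event row, and a statement in Section 6 of what the sample size can exclude, are optional.

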7.4.2. Interim Analyses and Data Monitoring

No interim analyses are planned.

7.4.3. Final Analysis and Publication of Study Results

The final analysis will be completed after all subjects have completed the study.

7.5. Multiple Testing Procedures

There will be no adjustments for multiplicity and no formal multiple testing procedures are to be implemented with this analysis plan.

7.6. Baseline Values

Baseline values are the values obtained prior to the dispensing of study lenses at the Dispensing Visit (Visit 2/Day 1). If the Day 1 value is missing or is not scheduled to be collected, any value collected prior to treatment administration (e.g., from the Screening visit) will be used as the baseline. For the Distance logMAR Visual Acuity assessment, the BCDVA obtained at the Screening visit is the baseline value.

8. SUMMARY OF STUDY DATA

8.1. Subject Disposition

A summary of the analysis sets includes the number and percentage of subjects by treatment group and overall for the following categories: subjects in the SP, the ITT Population, and the PP Population. All percentages will be based on the number of randomized subjects.

End of trial information will also be summarized in this table, including the number of subjects completing the study, the number of subjects who prematurely discontinued the study with reasons for withdrawal, the number of subjects completing the study device dosing, and the number of subjects who prematurely discontinued lens wear with reasons for lens discontinuation.

A by-subject data listing of study completion information including the reason for premature study withdrawal or lens wear discontinuation, if applicable, will be presented.

8.2. Protocol Deviations

Important protocol deviations will be determined by a Sponsor review of the data prior to database lock. The Sponsor or designee will be responsible for producing the final deviation file; this file will include a description of the protocol deviation and clearly identify whether this violation warrants exclusion from the PP Population. This file will be finalized prior to database lock.

Protocol deviations will be presented in a by-subject data listing.

8.3. Demographics and Baseline Characteristics

Subject demographic data and baseline characteristics will be tabulated and summarized descriptively by treatment group and overall. The demographic data and baseline characteristics will be summarized for the ITT, Safety, and PP Populations.

The demographics consist of age (year), sex, race, and ethnicity. Age will be summarized using descriptive statistics. The number and percentage of subjects by sex, race, and ethnicity will be presented. Percentages will be based on the total number of subjects in the study population presentation.

The following baseline lens use characteristics will be summarized for each eye using descriptive statistics or categorically as applicable:

- Contact lens use (daily or extended wear)
- Average number of days worn per week
- Average daily wearing time (hours)

- Lens wear (full time, part time, occasionally, or socially)

Demographics and baseline characteristics, including all baseline lens use data, will be presented in by-subject listings.

8.4. Medical History

Ocular and general medical and surgical history will be coded using the MedDRA Version 26.1.

Ocular and general medical history data including specific details will not be tabulated but will be presented in by-subject listings.

Contact lens history and use will not be tabulated but will appear in by-subject listings.

8.5. Prior and Concomitant Medications

A concomitant medication is defined as any medication taken on or after the day of first exposure to study device. The number and percentages of all concomitant medications will be summarized by treatment group, Anatomical Therapeutic Chemical (ATC) level 4, and PT. The total number of concomitant medications and the number and percentages of subjects with at least 1 concomitant medication will be summarized by treatment group.

Prior medications are defined as any medication that has a start and stop date prior to the day of first exposure to study device. Prior medications will be summarized the same way as for concomitant medications.

Prior and concomitant medication summaries will be performed using the SP.

8.6. Study Device Exposure

The number of study lens exposure weeks will be calculated for each subject in the SP as the last date of study lens wear – date of lens dispensing + 1.

The average number of days per week the lens was worn and the average daily wearing time will be determined from the averages collected at each visit. Data will be collected separately for each eye.

The number of study lens exposure weeks will be tabulated and summarized descriptively by treatment group. The average number of days per week the lens was worn and the average daily wearing time will be summarized descriptively by treatment group and eye.

Lens exposure data will be presented in by-subject listings.

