	
20. History of any corneal surgery (eg, refractive surgery or therapeutic) in either eye
 
21. Any systemic disease currently affecting ocular health or which, in the Investigator's opinion, may have an effect on ocular health in either eye during the course of the study
 
22. Allergy to any component in the study care products
 
23. Meet any of the following criteria:
 
a. Subject is an employee of the investigative siteb. Subject or a member of the subject's household is an ophthalmologist, an optometrist, an optician, or an ophthalmic assistant/technicianc. Subject or a member of the subject's household is an employee of a manufacturer of contact lenses or contact lens care productsd. Subject or a member of the subject's household is an employee of a market research firm
Planned study period and duration of treatment:	The duration of lens wear (and duration of study participation) will be approximately 90 days.
Test lens:	
The Deseyne (vifilcon C) investigational spherical soft hydrophilic lens is proposed to be indicated for the optical correction of refractive ametropia (myopia and hyperopia) in phakic and/or aphakic persons with non-diseased eyes with up to and including 1.00 D of astigmatism that does not interfere with VA.
 
• Sphere power: -12.00 to +7.00 D• Diameter: 14.1 mm• Base curve: 8.6 mm• Material: vifilcon C
Control lens:	
1-Day Acuvue Moist (etafilcon A) daily disposable soft contact lens (Vistakon):
 
• Sphere power: -9.00 to +6.00 D• Diameter: 14.2 mm• Base curve: 8.5, 9.0 mm• Material: etafilcon A

Schedule of study visits:	Visit Number	Visit Name	Target	Acceptable Visit Range
	1	Screening Visit	None	Day -30 to -7
	2	Dispensing Visit	Day 1	Not applicable
	3	1-Week Visit	Day 8	Day 5–9
	4	1-Month Visit	Day 31	Day 27–35
	5	2-Month Visit	Day 61	Day 54–68
	6	3-Month/Exit Visit	Day 92	Day 91–101
Primary effectiveness endpoints:	
There will be 2 primary effectiveness endpoints for the study:
 
 1. Change from baseline to each post-baseline visit in distance logMAR VA by eye 2. Number and percentage of subjects, where there is no more than a 5–logMAR letters read loss from baseline (change from baseline in number of letters read ≥ -5). This is calculated by eye at each post-baseline visit. 			

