7.3.3. Handling of Early Termination Visit Information

In the event that a subject is terminated early from this study, the early termination data will be assigned to the closest visit. If the closest visit has valid data, the early termination data will be assigned to the next available visit, and treated as observed data for that visit in the imputation procedures described above.

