12. APPENDICES

12.1. List of Planned Tables

The list of planned tables includes all of the *main* tables to be presented

Table	Description of Table	All	Safety	ITT	PP
14.1.1.1	Subject Disposition	X			
14.1.2.x	Demographics and Baseline Characteristics		X	X	X
14.1.3.x	Baseline Lens Characteristics		X	X	X
14.1.4.1	Prior Medications		X		
14.1.4.2	Concomitant Medications		X		
14.1.5	Study Device Exposure		X		
14.2.1.x	Distance logMAR Visual Acuity by Visit and Eye			X	X
14.2.2.x	Subjects With No More Than 5 Letters Read Loss From Baseline in Distance logMAR Visual Acuity by Visit and Eye			X	X
14.2.3.x	Symptoms/Complaints and Subjective Assessments by Visit and Eye			X	X
14.2.4.x	Lens Wettability, Centration, and Movement by Visit and Eye			X	X
14.2.5.x	Lens Deposits by Visit and Eye			X	X
14.3.1.1	Treatment-Emergent Adverse Events (TEAE) by System Organ Class and Preferred Term		X		
14.3.1.2	Serious Treatment-Emergent Adverse Events (TEAE) by System Organ Class and Preferred Term		X		
14.3.1.3	Treatment-Emergent Adverse Events (TEAE) Leading to Withdrawal From the Study by System Organ Class and Preferred Term		X		
14.3.1.4	Treatment-Emergent Adverse Events (TEAE) Leading to Lens Wear Discontinuation by System Organ Class and Preferred Term		X		

Table	Description of Table	All	Safety	ITT	PP
14.3.3	Eyes With Slit Lamp Findings Grade >2 at Any Follow-up Visit		X		
14.3.4	Conjunctival Hyperemia by Visit and Eye		X		
14.3.5	Keratometry at Final Visit by Eye		X		
14.3.6	Spherocylindrical Refraction at Final Visit by Eye		X		
14.3.7	Corneal Fluorescein Staining by Visit and Eye		X		
14.3.8	Best-corrected Distance Visual Acuity (BCDVA) at Final Visit by Eye		X		
14.3.9	Lens Discontinuation Rate at Each Follow-up Visit by Eye		X		
14.3.10	Use of Unpreserved Lubricant Eyedrops or Artificial Tears by Visit and Eye		X		

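### SAP 8.6 calls a day count 'weeks': followed as written, a completer's lens exposure reads about 92 weeks instead of about 13

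*SAP*

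**What the plan says.** SAP 8.6 gives the derivation: "exposure weeks will be calculated for each subject in the SP as the last date of study lens wear – date of lens dispensing", with 1 added. The same section then plans the output: "The number of study lens exposure weeks will be tabulated and summarized descriptively by treatment group". SAP 12.1 lists this as Table 14.1.5, on the safety population.

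The variable is used again in SAP 10.3: "The time to discontinuation will be based on the study lens exposure weeks defined in Section 8.6". The listed discontinuation output is Table 14.3.9, "Lens Discontinuation Rate at Each Follow-up Visit by Eye".

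The protocol synopsis sets the time scale: "The duration of lens wear (and duration of study participation) will be approximately 90 days". Dispensing is Day 1. The exit visit is targeted at Day 92, with a range of Day 91–101.

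On eyedrops, a separate matter, SAP 10.3 assesses use by "counting the number of drops recorded in the OTC Artificial Tears Log for the period between each visit", and SAP 12.1 lists the result as Table 14.3.10. For subjects who stop early, SAP 7.3.3 says that "the early termination data will be assigned to the closest visit", or to the next available visit if the closest one already has valid data.

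**The concern.** The formula and its label are in different units. Subtracting calendar dates gives days, and adding 1 is the usual way to count both end dates. The SAP calls the result weeks when it defines the variable, when it tabulates it and when it reuses it in 10.3. No conversion appears anywhere.

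What is at stake is the absolute exposure reported. The SAP is what the derived datasets are programmed and validated against. One programmer can follow the formula and another the label, and each can defend the result. If the formula is followed, the exposure table is wrong by a factor of 7. If someone corrects it silently, the analysis departs from the SAP without a record.

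The eyedrop point is not an arithmetic error. Raw counts over periods of unequal length cannot be compared across visits, and within a visit they carry noise from permitted visit timing.

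**Working it through.** The documents state no exposure figure, so there is none to reproduce. The check is date arithmetic.

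**Inputs.** Dispensing on Day 1 (SAP 7.6; protocol synopsis). Visit targets of Days 8, 31, 61 and 92, and an exit range of Day 91–101 (protocol synopsis). Planned wear of about 90 days (protocol synopsis). Assumption: a completer's last day of wear is the exit visit day.

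**Formulas.** As written: last wear day − dispensing day + 1. In weeks: (last wear day − dispensing day + 1) / 7.

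| Last wear day | As written, labelled weeks | Actual weeks |
|---|---|---|
| 8 | 8 − 1 + 1 = 8 | 8/7 = 1.14 |
| 31 | 31 | 4.43 |
| 61 | 61 | 8.71 |
| 91 | 91 | 13.00 |
| 92 | 92 | 13.14 |
| 101 | 101 | 14.43 |

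The planned 90 days is 90/7 = 12.86 weeks, so any value near 92 weeks is impossible. If last wear falls the day before a Day 92 exit, the values are 91 and 13.00, and nothing changes in substance.

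**A more generous reading.** Suppose the date difference is taken as already in weeks. The added 1 then becomes a whole week: 91/7 + 1 = 14.00 for a Day 92 exit, against 13.14. The text fails on this reading too, by 0.86 week.

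**Effect on discontinuation.** Time to discontinuation inherits the factor of 7 directly. The visit-level rate in Table 14.3.9 is affected only if week cut-offs on this variable are used to place discontinuations at visits, which the SAP neither states nor excludes. If they were, last wear on Day 10 is 10/7 = 1.43 weeks, between the 1-Week and 1-Month targets (1.14 and 4.43). Read as 10 weeks, it would fall between the 2-Month and 3-Month targets (8.71 and 13.14).

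**Eyedrops (separate).**
- Periods between target days: 8 − 1 = 7, 31 − 8 = 23, 61 − 31 = 30 and 92 − 61 = 31 days.
- 1-Month to 2-Month within the windows (Day 27–35 and Day 54–68): 54 − 35 = 19 to 68 − 27 = 41 days.
- 2-Month to Exit within the windows: 91 − 68 = 23 to 101 − 54 = 47 days, a ratio of 47/23 = 2.04.
- The 1-Week window differs between the documents (Day 5–9 in the protocol, Day 6–10 in SAP Table 1), so periods touching that visit are given at target only.
- The documents give no drop rate. At an assumed constant 2 drops per day, for illustration only, the counts at target are 14, 46, 60 and 62. The Exit count alone runs from 2 × 23 = 46 to 2 × 47 = 94.
- Early termination can shorten the period further. Take a subject seen on Day 31 who stops on Day 40. By target day the closest visit is 1-Month (40 − 31 = 9 days away, against 61 − 40 = 21). That visit already has data, so the record moves to 2-Month. If SAP 7.3.3 is applied to the eyedrop count, the 2-Month entry then covers 9 days instead of 30.

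**The case against.** The strongest reply is that this is an editorial slip. The intended unit is clear from the label, 92 weeks in a 90-day study would be noticed, and SAP 7.3.6 plans validation of datasets and tables. Exposure is not an endpoint, both arms are scaled alike, and no effectiveness or slit lamp result depends on it. All of this is fair, and it limits the importance of the point. It does not make the rule correct: validation against this text could confirm either result.

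On discontinuation, SAP 10.3 says it is assessed at each scheduled follow-up visit, optionally at unscheduled ones, and mentions no week cut-offs. SAP 12.1 and 12.3 list no table or figure of time to discontinuation, although 12.1 covers only the main tables. This largely stands. The Day 10 example is conditional, since the SAP says when discontinuation is assessed but not how time on lens or an unscheduled-visit event maps to a visit's rate. The certain effect is on the definition of time to discontinuation, not on Table 14.3.9.

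On eyedrops, a count between visits is a legitimate summary. Table 14.3.10 is presented by visit, both arms follow the same schedule, and the daily log will be listed. Unequal periods across visits therefore do not bias the comparison of arms at a given visit. That stands. The two-fold spread also needs two subjects at opposite window extremes at both visits, so it is an outer limit and not a typical spread. What remains is added noise and a loss of comparability across visits, which is why the change is offered as optional.

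**Conclusion.** The concern holds. SAP 8.6 is wrong as written: its formula returns days and its label says weeks. Followed literally, it overstates exposure by exactly 7: 92 instead of 13.1 weeks at the exit target, and 91–101 instead of 13.0–14.4 across the exit window. These figures assume wear up to the exit visit, and one day less does not alter the conclusion.

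The certain consequences are confined to Table 14.1.5 and the time-to-discontinuation variable. Any effect on the visit-level discontinuation rate depends on an assignment rule that the SAP does not give. The correction should be made before the exposure dataset is programmed, but it does not threaten the study's main results. The eyedrop point is a possible improvement in reporting, not an error.

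**What to change.** In SAP 8.6, define exposure weeks as (last date of study lens wear − date of lens dispensing + 1) / 7. Section 10.3 then needs no change of unit. Alternatively, keep the formula and rename the variable exposure days in both 8.6 and 10.3, with a matching label in Table 14.1.5. Either way the cost is a line or two of SAP text and no new data.

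Optionally, in SAP 10.3 and Table 14.3.10, also summarize drops per day (drops recorded divided by the days in the period covered), and keep the raw counts in the listing. This adds one derived variable from a log that is already kept daily. It also handles early-termination records, because the divisor is the period actually covered.
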